**Safety Considerations:**

Overall, patient risk would be considered minimal.

The risks of phlebotomy coupled with treatment and management are:

1. Arterospasm, Hematoma – sterile compression bandage will be done to achieve hemostasis monitoring of vital signs digital pulse oximetry to ensure perfusion of tissues, blood transfusions, Vascular Surgeon consultation for brachial artery repair, and/or luminal dilatation.
2. Nerve damage/injury- Orthopaedic management of possible injury to median nerve, evaluation, and follow-up in the clinic, and possible anti-inflammatory medications for nerve inflammation.
3. Infection- Debridement, microscopy, culture, and sensitivity as well as initiating empirical broad-spectrum antibiotics, and monitoring for signs of sepsis. If febrile or septic shock admission to hospital and commencement of intravenous fluids, intravenous antibiotics with possible ICU intervention.
4. Low risk: Phlebotomy: Vascular spasm, hematoma, local infection, Medium Risk Phlebotomy: nerve damage/injury (unlikely), Empagliflozin: urinary tract infections, fungal infections, (rare-occasional, usually not life-threatening), Serious Risk Phlebotomy: hand surgery (exceedingly rare), Empagliflozin: diabetic ketoacidosis, Fournier's gangrene, and hypoglycemia (very rare).

The study will be by the summary of risks and risk-reduction strategies outlined in Table 8 in the WHO Guidelines on Drawing Blood: Best Practices in Phlebotomy. Any serious adverse events (SAEs) will be recorded as per the Bleeding Academic Research Consortium (BARC) group definitions and reported to the Ethics Committee of the University of the West Indies within 24 hours. The patient will receive health care per the participating institution's guidelines and policies i.e. Cardiology Department at EWMSC, Mt. Hope, Trinidad & Tobago.

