## **Rationale and Background:**

Dual antiplatelet therapy (DAPT) with aspirin and clopidogrel represents the standard of care for the prevention of recurrent ischemic events in patients undergoing percutaneous coronary intervention (PCI). For more than 20 years, dual antiplatelet therapy with aspirin and Clopidogrel has remained the cornerstone of treatment for patients with acute coronary syndrome (ACS). However, some patients have impaired clopidogrel response and thus persist with high on-treatment platelet reactivity (HPR) resulting in an increased risk of atherothrombotic events. The boxed warning added to the clopidogrel label underscoring the potential risk of adverse cardiovascular outcomes among patients with a “poor metabolizer” genotype and advocating the use of other antiplatelet medications or alternative dosing strategies for these patients has led to investigations of treatment options associated with more optimal platelet inhibition. These include switching to a novel generation P2Y12 inhibitor (e.g. prasugrel or ticagrelor).

Sodium-glucose transport 2 inhibitors (SGLT2i) such as empagliflozin have been found to reduce the risk of hospitalization for heart failure and death in individuals with type 2 diabetes, although the exact mechanism behind this effect is not yet fully understood. It is also uncertain whether empagliflozin's impact on platelet function plays a role in its ability to decrease cardiovascular mortality. SGLT2i therapies have become increasingly important for T2DM patients, as evidenced by major clinical trials like EMPA-REG OUTCOME and DAPA-HF, which have shown a significant reduction in major adverse cardiovascular events (MACE). The exact mechanisms responsible for these positive cardiovascular outcomes are still being investigated. It is currently unknown whether SGLT2 inhibition has an antiplatelet effect. However, a pilot study has shown that empagliflozin does have a greater antiplatelet effect than traditional treatments for T2DM patients with coronary artery disease (CAD). This study is important for its potential to improve both efficacy and safety in the treatment of T2DM.

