#### *Exclusion criteria*

Patients are ineligible to participate if any of the following criteria are met:

1. presence of active internal bleeding or history of bleeding diathesis or clinical findings associated with an increased risk of bleeding,
2. history of ischemic or hemorrhagic stroke, transient ischemic attack, intracranial neoplasm, arteriovenous malformation, or aneurysm,
3. history of clinical and/or hemodynamic instability,
4. within 1 month of placement of a bare metal stent,
5. within 30 days of coronary artery bypass graft surgery or PCI without a stent placed,
6. planned coronary revascularization,
7. treatment with fibrin-specific fibrinolytic therapy <24 h or non-fibrin-specific fibrinolytic therapy <48 h,
8. use of an oral anticoagulation agent or international normalized ratio >1.5,
9. body weight <60 kg,
10. age >75 years,
11. hemoglobin <10 g/dL,
12. platelet count <100×10^6/µL,
13. creatinine >2 mg/dL,
14. hepatic enzymes >2.5 times the upper limit of normal,
15. pregnancy and/or lactation.

The study will undergo a formal approval process by the Campus Ethics Committee (CEC) of the University of the West Indies (UWI) and all patients are to provide written informed consent before participating in the study. The trial will be conducted by the Declaration of Helsinki and the International Conference on Harmonization (ICH) Guidelines for Good Clinical Practice (GCP). Two clinical research associates (CRAs) will secure and assess the quality of the data and the university biostatistician will perform the data analysis after data lock. The CRAs will then deliver the database and the analysis results to the principal investigator (PI). Data will be coded per patient by first letter of first name, first letter of last name followed by numerical date of birth in the order of day, month, and year in a password-protected and encrypted

database program in the office of Lecturer [name] at the Department of Clinical Medicine office, [name], Eric Williams Medical Sciences Complex.

*Patient Interview and Case Report Form*

If a patient satisfies the selection criteria from the initial screening process, a physician or CRA-directed interview will then be administered. Demographic and anthropometric data will be recorded on a case report form (CRF). This will comprise the patient's medical and procedural history including any active medications.

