#### **Expected Outcomes of the Study:**

The information obtained from the study would be integral in developing antiplatelet strategies for patients with impaired platelet reactivity. It will advance knowledge in the field i.e. useful for baseline information and hypothesis generation for further studies within the scientific community. It will also determine if empagliflozin is an adjunct for non-response to the current armamentarium of antiplatelet therapies available in Trinidad and Tobago. This information can then reliably inform regulatory bodies e.g. Ministry of Health (MOH) to make additions to the national Chronic Disease Assistance Medication Program (CDAP) to include this as a possible adjunct to facilitate a more potent antiplatelet effect.

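### The protocol provides for recording serious adverse events only, so the infections it rates as the more frequent empagliflozin harms, and minor bleeding on dual antiplatelet therapy, have no stated route into the data

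*Combined protocol and SAP*

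**What the plan says.** **Recording rule.** Safety Considerations states: "Any serious adverse events (SAEs) will be recorded as per the Bleeding Academic Research Consortium (BARC) group definitions". It adds a 24-hour report to the ethics committee. Follow-up also speaks only of serious events.

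**Expected harms.** The same section grades the empagliflozin risks. Its middle tier holds "Empagliflozin: urinary tract infections, fungal infections, (rare-occasional, usually not life-threatening". Its top tier holds "Empagliflozin: diabetic ketoacidosis, Fournier's gangrene, and hypoglycemia (very rare". It opens with the statement "Overall, patient risk would be considered minimal". Hematoma appears only as a risk of phlebotomy, and no bleeding risk is listed for adding the drug.

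**Data collection.** Under Patient Interview and Case Report Form (printed after the exclusion criteria), "Demographic and anthropometric data will be recorded on a case report form (CRF", together with medical and procedural history and current medication. Blood Sampling, Phlebotomy names the VerifyNow P2Y12 assay as the one test repeated at the second week, and mentions no adverse-event enquiry there.

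**Intended use.** Expected Outcomes of the Study looks to the national drug-assistance programme adding "this as a possible adjunct to facilitate a more potent antiplatelet effect".

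**The concern.** The recording threshold sits above the events that the protocol itself expects most. An uncomplicated urinary or genital infection would usually not be serious, and the recording rule does not reach it.

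Bleeding matters more for this trial's question. If the hypothesis is right, platelet reactivity falls further in patients already taking aspirin and clopidogrel, and bleeding is the natural cost to look for. The exclusion criteria show that the investigators have bleeding in mind: they screen out active bleeding, bleeding diathesis, oral anticoagulation, low hemoglobin and low platelet counts. Yet the bleeding scale they cite is attached only to serious events.

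At stake is what a reader of the results can weigh. A report of stronger platelet inhibition with no infection or minor bleeding listed could mean that none occurred or that none was asked about. The plan as written would not let a reader tell which.

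**Working it through.** The plan gives no adverse-event rate and no safety precision figure, so there is no safety number to reproduce. The check is first a reading of each section, then arithmetic on assumed rates.

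**Step 1. Where could a non-serious event enter the data?**

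| Section | What it provides |
|---|---|
| Study Goals and Objectives | platelet function only |
| Patient Interview and Case Report Form | demographics, anthropometrics, history, medication |
| Blood Sampling, Phlebotomy | platelet test repeated at the second week; no event enquiry stated |
| Safety Considerations | serious events only |
| Follow-up | serious events only |
| Data Management and Statistical Analysis | no safety tabulation |
| Quality Assurance | no data safety and monitoring board |

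No section states a route.

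**Step 2. Threshold against expectation.** Infections are in the plan's middle tier, at its highest stated frequency for the drug. Ketoacidosis, Fournier's gangrene and hypoglycemia are in the top tier, at its lowest. The recording rule therefore aims at the less frequent group. The cited bleeding scale also supplies no definition for the non-bleeding serious events on that list.

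**Step 3. How many events might be involved?** Inputs from the documents: 10 days of treatment; n = 20 (Sample Size Calculation) or at least 16 (Data Management and Statistical Analysis). The allocation ratio is not stated, nor whether 20 is a total or per group. I take 10 exposed (20 in total, split equally) up to 20 exposed (one group, or 20 per group). Assumed, and not in the documents: a 10-day rate p of 1%, 5% or 10% for one type of non-serious event.

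Expected events = n × p. Chance of at least one = 1 − (1 − p)^n.

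| Exposed n | p = 1% | p = 5% | p = 10% |
|---|---|---|---|
| 10 | 0.1 expected; 1 − 0.99^10 = 9.6% | 0.5; 1 − 0.95^10 = 40.1% | 1.0; 1 − 0.90^10 = 65.1% |
| 20 | 0.2; 1 − 0.99^20 = 18.2% | 1.0; 1 − 0.95^20 = 64.2% | 2.0; 1 − 0.90^20 = 87.8% |

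For comparison, under recording of serious events only, assumed serious-event rates of 0.5% to 1% give 10 × 0.005 = 0.05 up to 20 × 0.01 = 0.2 expected events. The chance of recording any runs from 1 − 0.995^10 = 4.9% to 18.2%. A nearly empty safety record is then the likely result.

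**Step 4. What full collection could show.** With zero events of a given type, the exact two-sided 95% upper limit is 1 − 0.025^(1/n): 30.8% for 0/10 and 16.8% for 0/20. These limits depend on n alone. They bound what the proposed table can say and do not measure the recording gap.

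**The case against.** The strongest reply is that this argues from silence. The protocol says serious events will be recorded and does not say that others will not be. It commits to Good Clinical Practice, the case report form itself is not shown, and only its interview content is described. This stands as a limit on wording. A reader might infer that non-serious events are excluded by rule and will never be counted, and the documents do not support that. They support only that no provision is stated. A general commitment to good practice supplies no questions, timing or form field, so it does not ensure uniform capture.

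Second, the sentence tying serious events to a bleeding scale may be a loose way of saying that all bleeding will be graded. That is possible, and the text does not settle it. As written, its subject is serious events.

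Third, few events would be expected anyway. With 10 exposed patients and a rate of 1%, full collection would still find nothing about 90% of the time (100% − 9.6%). So low counts cannot be put down to the recording rule alone.

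Fourth, the plan has no safety objective and promises no safety result. The Rationale sentence "This study is important for its potential to improve both efficacy and safety in the treatment of T2DM" might be taken as a safety claim for this trial. It speaks only of potential and follows directly on a remark about a pilot study, so it does not bear that weight. The intended policy use in Expected Outcomes does stand, and it is reason enough to collect the information.

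**Conclusion.** The gap is real and should be closed before enrolment. The only stated recording rule covers serious events, and no section provides for non-serious adverse events or minor bleeding. The platelet-reactivity comparison itself is not affected.

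The size can be given only under assumption: for each type of non-serious event, 0.1 to 2.0 expected occurrences across 10 to 20 exposed patients at 10-day rates of 1% to 10%, with no stated place to record them. This rests on the assumed rates, on equal allocation where there are two groups, and on the unseen case report form holding no adverse-event page.

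Two stronger readings should be resisted. One is that the trial will report near-zero harm by construction: small numbers and 10 days of exposure contribute as well, and no harm report is promised. The other is that the zero-event limits refute the statement of minimal risk: that statement is a prospective judgement about taking part, not an inference from observed counts.

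**What to change.** In Safety Considerations, state that all adverse events, serious or not, are recorded from randomisation, or from the baseline visit if the design is single-group. First dose would not serve as the starting point, because the comparator group is not said to receive a study drug.

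At the existing second visit, ask every patient the same fixed case report form questions: any bleeding (graded at every level of the scale already cited), urinary symptoms, genital infection, and symptoms of hypoglycemia. In Data Management and Statistical Analysis, add one descriptive table of counts with exact confidence limits, by group if there are two groups. Keep the 24-hour report for serious events.

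Study Design describes an open-label study, while the methodology describes randomisation, a comparator group and blinding. These must be reconciled. If the study is open-label, the report should say that solicited symptoms are open to reporting bias.

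The cost is one form page, a few minutes per patient at a visit already planned, one table, and a higher reported event count. No added patients or visits are needed. The table should be labelled descriptive, because 10 to 20 exposed patients over 10 days cannot establish safety.

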***Follow-up:***

Patients will be informed of their results in person, or if unavailable via telephone. They will also be provided with a hard-copy report of their platelet function profiles. They will also be informed on a scheduled basis of the management plan for any serious adverse events (SAEs) that may have unfortunately occurred as a result of their direct participation in the study.

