**Data Management and Statistical Analysis:**

The patient information will be initially recorded on CRFs which will be stored in the Adult Medicine Unit locking file cabinets, located at the Department of Clinical Medical Sciences, University of the West Indies, St. Augustine. Data will be coded per patient by first letter of first name, first letter of last name followed by numerical date of birth in the order of day, month, and year in a password-protected and encrypted database program in the office of Lecturer [name] at the Department of Clinical Medicine office, [name], Eric Williams Medical Sciences Complex. Each CRF and study database will be reviewed by 2 CRAs to minimize error, and clean and reconcile any conflicting data. We will aim for  $n$  of least 16 patient profiles, see sample size calculations. Any missing information will be censored and

thus, not imputed. The study biostatistician will perform routine statistical analyses with SPSS v. 11.0 software (SPSS, Chicago, IL). Continuous variables are expressed as means  $\pm$  SD. Categorical variables are to be expressed as frequencies and percentages. Student's t-test will be used to compare continuous variables. Comparisons between categorical variables will be performed using the two-tailed Fisher's exact test or Pearson's  $\chi^2$  test, as appropriate. A p-value of  $< 0.05$  will be considered statistically significant. No adjustments for multiple comparisons will be made. Results will be reported as least-square mean  $\pm$  SEM for the detailed analyses.

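### The only rule for recording serious adverse events is a bleeding classification, which cannot classify the non-bleeding harms of empagliflozin and phlebotomy that the same section lists

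*Combined protocol and SAP*

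**What the plan says.** Safety Considerations contains the only instruction on how SAEs are to be recorded: "Any serious adverse events (SAEs) will be recorded as per the Bleeding Academic Research Consortium (BARC) group definitions". The same sentence requires them to be "reported to the Ethics Committee of the University of the West Indies within 24 hours".

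That section also lists the expected harms. Its tier of serious risks includes, for the study drug, "Empagliflozin: diabetic ketoacidosis, Fournier's gangrene, and hypoglycemia (very rare"). For infection after phlebotomy it foresees a severe course: "If febrile or septic shock admission to hospital and commencement of intravenous fluids, intravenous antibiotics with possible ICU intervention".

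Other sections touch on the subject without adding a recording rule:

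- The trial-conduct paragraph under Exclusion criteria commits the study to ICH GCP in general terms, and Quality Assurance repeats the GCP commitment.
- Follow-up says patients will be told of the "management plan for any serious adverse events (SAEs) that may have unfortunately occurred as a result of their direct participation".
- Data Management and Statistical Analysis says "Each CRF and study database will be reviewed by 2 CRAs to minimize error, and clean and reconcile any conflicting data", with no SAE criteria.
- Quality Assurance states that there will be no data safety and monitoring board.

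**The concern.** The recording rule and the list of harms do not match. The rule applies to SAEs of every kind but points to a scheme for bleeding only. Every empagliflozin harm that the protocol names lies outside that scheme.

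Two things are at stake. First, someone completing or checking a case report form has no written criterion for when a non-bleeding event is serious, or for how to enter it. Urinary and fungal infections show the difficulty: the protocol describes them as normally not threatening to life, which allows that some may be, but it does not say how to decide. Similar events could then be handled differently from one patient to the next, and the record would be least reliable for the study drug's own risks. Second, the 24-hour report starts only once an event has been called an SAE. With no monitoring board, the site record and that report are the main safety record the protocol describes.

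**Working it through.** No formula applies, and the plan gives no figure to reproduce. The check has two parts: whether the rule fits the harms listed, and whether another section supplies a rule that does.

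**1. Does the rule fit the harms?** Safety Considerations names the following distinct harms, with repeated mentions merged (for example, the two entries for vessel spasm).

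| Harm | Source | Bleed? |
|---|---|---|
| Arterial or vascular spasm | Phlebotomy | No |
| Hematoma | Phlebotomy | Yes |
| Nerve injury | Phlebotomy | No |
| Infection, possibly to septic shock | Phlebotomy | No |
| Hand surgery (serious tier) | Phlebotomy | Procedure, cause not stated |
| Urinary tract infection | Empagliflozin | No |
| Fungal infection | Empagliflozin | No |
| Ketoacidosis (serious tier) | Empagliflozin | No |
| Fournier's gangrene (serious tier) | Empagliflozin | No |
| Hypoglycemia (serious tier) | Empagliflozin | No |

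Counts:

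- All harms: 8 non-bleeding + 1 bleed + 1 procedure = 10.
- Empagliflozin harms: 5 named, 0 bleeds.
- Serious tier: 4 entries, of which 3 are non-bleeding conditions and 1 is hand surgery. As named, none of the 4 is a bleed.

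The serious-tier and empagliflozin counts matter most, because the rule governs serious events and empagliflozin is the drug under test. The count of 10 includes harms that the protocol itself ranks as low risk.

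**2. Does another section supply a rule?** Each mention of SAEs, safety, BARC or GCP in the supplied text was compared.

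| Section | What it covers | Gives a criterion for non-bleeding SAEs? |
|---|---|---|
| Safety Considerations | Recording by BARC; 24-hour report | No |
| Exclusion criteria, conduct paragraph | General ICH GCP commitment | Not linked to SAE recording |
| Exclusion criteria, case report form paragraph | Demographic and anthropometric data, history, medications | No |
| Follow-up | Informing patients | No |
| Data Management and Statistical Analysis | Form and database review, tests | No |
| Quality Assurance | General GCP commitment; no monitoring board | No |

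The BARC sentence is therefore the only explicit rule. The general GCP commitment is never tied to how SAEs are identified or recorded.

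**The case against.** The strongest reply is that the study has committed itself to GCP in two places, so a general definition of an SAE is already in force and the fault is one badly worded sentence. This narrows the point but does not remove it. No section links GCP to SAE recording, and the one explicit instruction names BARC; staff who follow the protocol as written would use BARC. If the GCP criteria were intended, the fix only states that intent.

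Other objections stand in part:

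- **Reporting is not lost.** The duty to record and report is worded for any SAE, and nothing excludes non-bleeding events. This is correct. The gap lies in how such events are identified and classified.
- **BARC suits this study.** Patients take aspirin and clopidogrel, and the study looks for added platelet inhibition, so bleeding is a natural harm to grade. This is also correct, and is the reason to keep BARC for bleeds.
- **Inconsistent recording is a prediction.** The protocol has the two research associates review and reconcile forms; it does not say who judges seriousness. The absence of a stated criterion is certain from the text. Its effect on the record is an inference.
- **The overall tally includes minor harms.** That is fair. The conclusion holds on the serious tier alone.
- **Some material is unseen.** The case report form and the attached consent file are not in the supplied text. The form may already have a general SAE field.

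**Conclusion.** The concern holds. The rule as written cannot classify the serious harms that the same section attributes to the study drug, and no other section of the supplied text provides one that can. All 5 named empagliflozin harms fall outside a bleeding classification, and so do 3 of the 4 serious-tier entries, with hand surgery undetermined because its cause is not given.

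The consequence is limited. The protocol aims for at least 16 patients in one section and gives n = 20 in another, each treated for 10 days, so few events are expected. The matter is consistent safety recording; it does not bear on the comparison of platelet reactivity units. It should be corrected because patients carry the listed risks, there is no monitoring board, and the correction is almost free.

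The conclusion rests on two assumptions: that BARC covers what its name says, and that the unseen form and attachments contain no overriding SAE rule.

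**What to change.** In Safety Considerations:

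1. Define and record all SAEs, whatever their type, by the seriousness criteria of the ICH GCP guideline that the protocol already adopts. A reference to that guideline is enough.
2. Restrict BARC to an additional grade for bleeding events.
3. State that the existing 24-hour Ethics Committee report applies to every SAE so defined. This confirms the present wording and adds no new duty.
4. Add a line for these events to the case report form if it does not already have one.

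The cost is one or two sentences, at most one form line, and slightly more recording by the research associates. Visits, sample size, analysis and patient management do not change.
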